9.1.5. Severity of Adverse Event

A summary of TEAEs by severity will be presented in a table. The severity that will be presented represents the most extreme severity captured on the case report form (CRF) page. The possible severities are “Mild,” “Moderate”, “Severe”, “Life-threatening” and “Death”. In the TEAE severity table, if a subject reported multiple occurrences of the same TEAE, only the most severe level will be presented. TEAEs that are missing severity will be presented in tables as “Severe” but will be presented in the data listing with a missing severity. Percentages will be calculated out of the number of subjects in the FAS.

The TEAE data will be categorized and presented by SOC, PT, and severity, similar to that described in [Section 9.1.1](#) .

9.1.6. Serious Adverse Events

The seriousness of an AE should be assessed by the investigator independently from the severity of the AE. An AE is considered a serious adverse event (SAE) if at least one of the following conditions applies:

- Death: An AE that results in death during the active study period or within 90 days following study drug administration. In addition, a reported death at any time post-study that is thought to be related to study drug administration.
- Life-threatening AE: An AE that places the subject, in the view of the investigator, at immediate risk of death from the event as it occurred (i.e., this does not include a reaction that, had it occurred in a more severe form, might have caused death).
- Permanent, persistent, or significant disability: A disability is defined as any substantial disruption of a person’s ability to conduct normal life functions.
- Inpatient hospitalization or prolongation of existing hospitalization: In general, hospitalization refers to admission of a subject into a hospital for at least a 24-hour stay. Hospitalizations for routine blood transfusions, hospitalization for an elective or diagnostic procedure, or surgery for a pre-existing condition that has not worsened, are not considered SAEs. Emergency room visits that do not result with admission are not considered as SAEs.
- A congenital anomaly/birth defect: A fixed, permanent impairment established at or before birth.
- Important medical event: Events that may not result in death, be life-threatening, or require hospitalization may be considered SAEs when, based upon appropriate medical judgment, they jeopardize the subject and require medical or surgical intervention to prevent a life-threatening situation, hospitalization or death.
- Important medical events that may not result in death, be life-threatening, or require hospitalization may be considered SAEs when, based upon medical judgment, they

may jeopardize the subject and may require medical or surgical intervention to prevent one of the outcomes listed above.

SAEs will be presented in a table. Treatment-emergent SAEs by relationship to study drug will be presented in a table. A treatment-related treatment-emergent SAE is a treatment-emergent SAE with any relation to study drug other than “Not Related” or “Unlikely”. Treatment-emergent SAEs that are missing a relationship will be presented in the table as “Related” but will be presented in the data listing with a missing relationship. At each level of subject summarization, a subject is counted once if the subject reported one or more events. Percentages will be calculated out of the number of subjects in the FAS.

The treatment-emergent SAE data will be categorized and presented by SOC and PT, similar to that described in [Section 9.1.1](#).

9.1.7. Adverse Events Leading to Treatment Discontinuation

A summary of TEAEs with a study drug action taken of “Drug Withdrawn” will be presented in a table separately for Ad-RTS-hIL-12, veledimex and cemiplimab. At each level of subject summarization, a subject is counted once if the subject reported one or more events. Percentages will be calculated out of the number of subjects in the FAS within the subgroup category.

The summary of TEAEs with a study drug action taken of “Drug Withdrawn” will also be presented in descending order of frequency from the SOC with the highest total incidence to the SOC with the lowest total incidence. Within each SOC, the PTs will be presented in alphabetical order.

9.1.8. Death

A summary of AEs where the answer to “Outcome” is “Fatal” will be presented in a table. At each level of subject summarization, a subject is counted once if the subject reported one or more events. Percentages will be calculated based on the FAS.

The summary of AEs where the answer to “Outcome” is “Fatal” will also be presented in descending order of frequency from the SOC with the highest incidence to the SOC with the lowest incidence. Within each SOC, the PTs will be presented in alphabetical order.

All subjects who have an AE with an outcome of “Fatal” will be presented in a listing. The listing will include the primary cause of death and the number of days elapsed between (day -7) and death.

9.2. Clinical Laboratory Evaluations

Laboratory assessments will be performed by a central laboratory. All summaries will be based on the units provided by the central laboratory, no conversion will be done.

Summary tables will be presented for clinical laboratory tests with numeric values for subjects in the FAS. Observed results at each visit will be presented.

All relevant clinical laboratory tests will be classified as Low, Normal, and High, or Normal/Abnormal according to the normal ranges. This categorical data will be summarized in shift tables comparing the results at each scheduled post-baseline visit with those at the baseline visit. Extreme post-baseline results will also be summarized.

When there are multiple values within a visit for a particular laboratory variable, the worst value will be taken (worst being the smallest value for criteria below a certain threshold or the largest value for criteria above a certain threshold). If a subject has a value below the threshold and above the threshold, the value furthest from the threshold will be chosen.

9.2.1. Hematology

The following laboratory tests will be included: complete blood count (CBC), including white blood cell (WBC) count with differential, red blood cell (RBC) count, hematocrit, hemoglobin, red blood cell indices, mean corpuscular volume (MCV), and platelet count. All hematology data by will be presented in a listing.

9.2.2. Serum Chemistry

The following laboratory tests will be included: Aspartate transaminase (AST), Alanine transaminase (ALT), lactate dehydrogenase (LDH), alkaline phosphatase (ALP), lipase, amylase, creatinine, total bilirubin, total protein, albumin, blood urea nitrogen (BUN), glucose, sodium, potassium, chloride, calcium, phosphorus, and bicarbonate. All chemistry data by subject will be presented in a listing.

9.2.3. Urinalysis

The following laboratory tests will be included: appearance, pH, specific gravity, glucose, protein/albumin, blood, ketones, bilirubin, nitrates, and leukocyte esterase. In addition, a microscopic exam for casts, crystals and cells may be done if indicated. All urinalysis data by subject will be presented in a listing.

9.2.4. Coagulation

The following laboratory tests will be included: activated partial thromboplastin time (aPTT) or partial prothrombin time (PTT) and prothrombin time (PT) or International normalized ratio (INR). The acute phase reactants include erythrocyte sedimentation rate (ESR) and C-reactive protein (CRP). All coagulation data by patient will be summarized and will be presented in a listing.

9.3. Vital Sign Measurements

Originally, all vital sign data by patient were planned for data summarization. Vital sign measurements are obtained for: height (cm), weight (kg), systolic and diastolic blood pressure (mmHg), heart rate (bpm), respiratory rate (breaths/minute) and temperature (°C).

The conversion for temperature is as follows:

- Temperature (°C) = (Temperature (°F) - 32) x (5/9).

Summary Listings for vital sign data include:

- the observed results for each scheduled visit.
- the change from baseline for each scheduled post-baseline visit. for:
 - systolic blood pressure (mmHg), diastolic blood pressure (mmHg), temperature (°C), pulse (bpm), respiration (breaths/minute) and weight for subjects in the FAS.

See variables under [Section 10.6](#) under Section 10 describing the changes to the planned analysis.

9.4. Physical and Neurological Examination

Originally, all physical and neurological examination data by patient were planned for data summarization along the lines of the following. In general,

- Physical examination data were to be provided in patient listings.
- Results of the targeted neurological exam were also to be listed and summarized.
- Clinically significant abnormalities that are identified during physical examinations were to be reported as adverse events.
- The disposition of each physical examination (whether performed or not) and the date the physical examination was performed was to be provided in individual patient listings.

A table was being planned to produce a summary of the physical examination results for the FAS. Each visit captures the status of a body system and any finding associated with the body system as normal, abnormal, or not done. The summary was planned to include the number and percentage of subjects with each physical examination outcome for the following body systems: skin, head, eyes, ears, nose, and throat (HEENT), respiratory, cardiovascular, gastrointestinal, endocrine/metabolic, genitourinary, neurological, blood/lymphatic, musculoskeletal and other. Physical examination results for all subjects were also planned for presentation in listings.

See variables under [Section 10.6](#), a subsection under Section 10 describing the changes to the planned analysis.

9.5. Electrocardiogram

Originally, electrocardiogram data by patient were planned for data summarization along the lines of the following. All subjects were to have a standard 12-lead electrocardiogram (ECG) performed during the study as clinically indicated. QT intervals were to be corrected according to the Bazett and Fridericia's formula. For summarization, results were to be converted into Bazett's correction. Electrocardiogram data for all subjects were to be presented in a listing.

The ECG interpretations was to be summarized in shift tables comparing the ECG values of each post-baseline visit with the value at the baseline visit for the FAS. In addition, the worst post-baseline ECG value was to be compared with the value at the baseline visit (with worst of all being Abnormal Clinically Significant and best being Normal).

Summary tables presenting observed values and changes from baseline were to be presented for heart rate (bpm), PR Interval (msec), RR Interval (msec), QRS Duration (msec), QT Interval (msec), QTcB Interval (msec) for subjects in the FAS. Changes from baseline to each scheduled post-baseline visit will be presented.

See variables under [Section 10.6](#) a subsection under Section 10 describing the changes to the planned analysis.

10. CHANGES TO THE PLANNED ANALYSIS

10.1. Transition to Describe Statistical Considerations implemented in Support of Producing an Abbreviated Study Report.

Originally, this SAP was being planned to support the creation of a full clinical trial study report (CSR). The decision to modify the final CSR based on a full CSR assumption to what is now being planned as an abbreviated CSR has led to the changes of this SAP which are summarized below.

As originally envisioned in the study Amendment 2 (08Jan2020) of the protocol, the following analyses described previously in Section 8 will not be included as part of the final statistical analysis.

10.4. Other Efficacy Endpoints

See original preplanning for KPS under [Section 8.4](#) of other efficacy endpoints. Originally planned, changes from baseline at each scheduled visit may not be performed to summarize descriptive statistics.

[REDACTED]

10.6. Other Endpoints Captured on the eCRF

The abbreviated CSR will not include the production of descriptive statistics and listings for the following preplanned assessments.

10.6.1. Vital Sign Measurements

See original preplanning under Vital Sign Measurements in [Section 9.3](#) .

10.6.2. Physical and Neurological Examination

See original preplanning under Physical and Neurological Examination in [Section 9.4](#) .

10.6.3. Electrocardiogram

See original preplanning under Electrocardiogram in [Section 9.5](#) .

11. GENERAL METHODS FOR PERFORMING STATISTICAL ANALYSES AND DATA HANDLING CONVENTIONS

The data conventions for preparing applicable tables and data listings for combining the data for all treated FAS subjects (n=40) are as follows:

11.1. Missing Data

- No imputations for missing or partial data will be made
- In analyses presented over time by visit, no imputations will be performed on missing data.
- All analyses will be based on observed data only without protocol deviations and violations.
- The effective sample sizes at each assessment visit will be based on the total number of subjects with non-missing data for the parameter of interest at that visit.

Unless otherwise specified,

- percentages will be calculated based on the number of patients with non-missing data as the denominator.
- A missing values category will also be defined to ensure all subjects are accounted for in prespecified populations for analyses
- In general, other than for partial dates, missing data will not be imputed and will be treated as missing.

The algorithms for imputation of partial dates vary depending on the parameter. These will be provided in the programming specifications that will be prepared for this study.

When applicable, unless otherwise specified, the following general imputation rules will be used for a missing date in the assessment of an event:

- If all parts of the date are missing, the date will not be imputed.
- In the case where only the start day of an event is missing, it will be replaced by the start day of study treatment if the event occurs in the same month and year. Otherwise, it will be replaced by the first of the month.
- If the stop day is missing, the stop day of the event will be replaced by the stop day of study treatment. Otherwise, the last day of the month will be used to replace the missing stop day.
- If both the start day and month of an event are missing, the start day and month will be replaced by the start day and month of study treatment if the event and the start of the treatment occur in the same year; otherwise, it will be replaced by 1st of January.
- All imputed dates must be prior to the dates of withdrawal of consent, lost to follow-up, and death.

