4.5.2. Full Analysis Set (FAS)

The Full Analysis Set (FAS) includes every subject who received at least one dose of any study drug recorded in the Data Management (DM) database excluding screen failures.

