4.5.3. Per Protocol (PP)

The per protocol population will comprise subjects who have received Day -7 of cemiplimab, the injection of Ad-RTS-hIL-12 with at least one post IL-12 dose of veledimex, at least one post IL-12 dose of cemiplimab (e.g., Day 15), and who have not had a major protocol deviation for which the key efficacy endpoints could be regarded as confounded or uninterpretable. Subjects who have had minor protocol deviation(s) that are thought not to impact efficacy will be included in this analysis population. Estimates of the overall OS hazard rate, the OS at prespecified timepoints, PFS and the ORR will be based on the PP population.

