4.5.4. Evaluable Safety Population (ESP)

The ESP is a subset of the FAS. Regardless of major protocol deviations, these subjects have received at least one of the following:

- Day -7 of cemiplimab,
- the injection of Ad-RTS-hIL-12 with at least one post IL-12 dose of veledimex,
- and at least one post IL-12 dose of cemiplimab (e.g., Day 15).

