4.7.2. Protocol Deviations

A protocol deviation is any change, divergence, or departure from the study design or procedures defined in the protocol. Important protocol deviations are a subset of protocol deviations that may significantly impact the completeness, accuracy, and/or reliability of the study data or that may significantly affect a subject's rights, safety, or well-being. In general, no subject was planned to be removed from any analysis population because of a protocol deviation.

In accordance with ICH E3, patient eligibility violations and important post- treatment protocol deviations will be identified and listed by patient and study center. Major deviations that are considered to potentially impact the efficacy or safety analyses will be tabulated. Important protocol deviations will be identified prior to database lock. Protocol deviations will be listed and summarized by type.

- Deviation from inclusion/exclusion criteria.
- Withdrawal criteria met during the study, but subject was not withdrawn.
- Prohibited concomitant medications.
- Treatment deviation.
- Other protocol deviation.

All protocol deviations will be categorized as either major or minor. The list of protocol deviations along with whether the deviation is classified denoting a major or minor categorization will be finalized prior to database lock.

Major protocol deviations will be presented in a summary table by protocol deviation category for the FAS. Protocol deviations will be presented in a listing.

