9. SAFETY ANALYSIS

All analyses of safety will be conducted using the FAS. Abnormal laboratory test results, will be captured as Adverse Events (AE)s. Safety evaluations will use calculations to determine estimates of the incidence, intensity, and the type of AE and SAE's based on preferred term coding.

All clinical findings will be further inspected through a clinical review of relevant parameters including AEs, serious adverse events (SAEs), laboratory values (hematology, serum chemistry, and urinalysis), body weight, vital signs, physical examinations, and ECOG performance status. Where applicable the Safety will also be summarized using the ESP. Exposure to study drug and reasons for discontinuation of study treatment will be tabulated.

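### SAP 11.1 restricts every analysis to data free of protocol deviations, against the SAP's own population definitions; the restriction should be deleted so that 11.1 matches SAP 4.7

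*SAP*

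**What the plan says.** The sentence at issue is a bullet in SAP 11.1 (Missing Data): "All analyses will be based on observed data only without protocol deviations and violations". It carries no qualifier; the usual opening about exceptions specified elsewhere comes only later in 11.1 and introduces other bullets. Section 11 sets its own scope at the start: "The data conventions for preparing applicable tables and data listings for combining the data for all treated FAS subjects (n=40) are as follows".

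Elsewhere the SAP handles deviations through population membership:

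- SAP 4.5.2: "The Full Analysis Set (FAS) includes every subject who received at least one dose of any study drug". Deviations are not a criterion.
- SAP 4.5.3: the Per Protocol (PP) set takes subjects "who have not had a major protocol deviation for which the key efficacy endpoints could be regarded as confounded or uninterpretable", and adds "Subjects who have had minor protocol deviation(s) that are thought not to impact efficacy will be included in this analysis population".
- SAP 4.5.4, on the Evaluable Safety Population (ESP): "Regardless of major protocol deviations, these subjects have received at least one of the following".
- SAP 4.5.6: Completers must be free of major deviations.
- SAP 4.7.2: "no subject was planned to be removed from any analysis population because of a protocol deviation". The sentence opens by saying that this holds in general.
- SAP 9: "All analyses of safety will be conducted using the FAS".
- Protocol 9.5, repeated in SAP 4.1: every dosed subject enters the overall safety assessment.

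**The concern.** Section 11 is the general data-handling section, the place a programmer looks for rules that apply to all output. A filter stated there without exception reaches three analyses that matter: adverse events in the FAS, secondary overall survival in the FAS, and primary overall survival in the PP set, where 4.5.3 expressly keeps minor deviators.

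Safety and overall survival are the two parts of the primary objective. The trial is single-arm and unblinded, and SAP 4.7.2 finalises the major or minor label of each deviation only before database lock. Two incompatible rules on who is analysed leave room for a choice made after outcomes are visible.

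**Working it through.** No figure in the plan depends on this rule, so there is none to reproduce. The check is a comparison of text, followed by two small illustrations.

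**Step 1. What 11.1 does to each analysis set if applied as written**

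| Set or analysis | Rule in its own section | Effect of 11.1 |
|---|---|---|
| FAS (4.5.2) | All treated subjects | Deviating subjects or records removed |
| Safety (Section 9; protocol 9.5) | FAS; all dosed subjects | Same removal from the adverse event tables |
| Secondary overall survival (4.7.1, 8.2) | FAS | Same removal |
| Primary overall survival (4.5.3, 8.2) | PP, minor deviators kept | Minor deviators removed as well |
| ESP (4.5.4) | Major deviators kept | All deviators removed |

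The bullet speaks of data, so it could mean records and not whole subjects. That milder reading also conflicts with the FAS and safety rules, because the affected records of included subjects would still be left out.

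**Step 2. What was probably meant**

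SAP 4.7 has two separate bullets on the same subject. One says that analyses use the observed data and stops there. The other provides additional derived variables, defined with and without deviations, to see how much deviations influence the results. The 11.1 bullet looks like these two run together, with a side comparison turned into a filter.

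**Step 3. A subject the filter could catch**

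SAP 4.7.3, Table 2, lists as a relevant deviation a total dose of veledimex or cemiplimab below 80% of that expected. It makes no exception for doses withheld under the protocol. SAP 7.2.2 takes the expected number of capsules from the schedule of events. Protocol 10.10 (Tables 2 and 3) provides for withholding or stopping these drugs after severe toxicity.

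- Scheduled veledimex doses, Days 0 to 14: 15.
- Three doses missed: 12/15 = 80%, not below the limit.
- Four doses missed: 11/15 = 73%, below the limit.

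So a subject with four veledimex doses withheld for toxicity could be counted as a relevant deviator and, under 11.1, leave the adverse event tables.

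**Step 4. Precision, for illustration only**

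The number of subjects with any deviation is not given. Assume that 0%, 25% or 50% of the 40 are removed. With x events in n subjects, the exact (Clopper-Pearson) 95% limits are L = Beta⁻¹(0.025; x, n−x+1) and U = Beta⁻¹(0.975; x+1, n−x). The half-width is (U−L)/2, maximised over x. With no events, U = 1 − 0.025^(1/n).

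| Assumed share removed | n | Maximum half-width | Upper limit with 0 events |
|---|---|---|---|
| 0% | 40 | 0.162 | 8.8% |
| 25% | 30 | 0.187 | 11.6% |
| 50% | 20 | 0.228 | 16.8% |

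These figures show loss of precision only. They say nothing about bias.

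**The case against.** The strongest reply is that no careful programmer would apply the sentence as a filter. It sits among bullets on not imputing missing values. The same list asks that all subjects be accounted for in the prespecified populations. SAP 9.1.3 to 9.1.8 base their percentages on the FAS, and the table list in Appendix 2 names the full analysis population for the adverse event tables. The 4.7 bullets show the intent. On this view it is a stray phrase with governing text elsewhere.

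Much of that stands. A reader might infer that the safety tables will in fact lose their deviators; the specific passages make that unlikely. It does not make 11.1 harmless. Naming the population for a table does not settle which data within it are used, and the SAP has no rule of precedence.

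Other inferences also go too far:

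- **That 11.1, 4.7.2 and 4.5.3 form a three-way contradiction.** SAP 4.7.2 speaks only in general terms, which leaves room for the explicit PP exclusion in 4.5.3. The sentence out of line is the one in 11.1.
- **That the FAS would become a second per-protocol set.** PP also requires the Day -7 cemiplimab dose, the injection, and later doses of veledimex and cemiplimab. The FAS requires one dose of any study drug.
- **That medication for oedema would mark sicker subjects as deviators.** Protocol 11 and 11.1 direct or permit corticosteroids for this purpose, and protocol 10.10 allows limited bevacizumab to be considered after consultation.

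**Conclusion.** SAP 11.1 is wrong as written. Followed literally, it would remove deviating subjects or records from every analysis, in conflict with SAP 4.5.2, 4.5.3, 4.5.4, 4.7, 4.7.2 and 9 and with protocol 9.5. It is most likely a drafting error, and that is how it should be described.

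This conclusion rests on the text alone and needs no assumption about how many subjects deviated. The size of the effect cannot be stated: the half-widths above rest on assumed shares of 25% and 50%. A reader might also infer that the filter would flatter safety or survival. The documents do not show that deviations cluster in sicker subjects or in those with more toxicity. The withheld-dose example shows only a route by which an affected subject could drop out, so the direction of any bias is unknown as well.

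**What to change.** Make four small edits before database lock:

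1. In SAP 11.1, end the sentence after the word data, so that it says the same as the observed-data bullet in 4.7.
2. State once that a deviation affects only membership of the PP set, under 4.5.3, and of the Completers, under 4.5.6. Naming PP alone would create a new conflict with 4.5.6.
3. In SAP 4.7.2, name those two sets as the exceptions to the general policy.
4. Keep any comparison with and without deviators as a labelled sensitivity analysis, in line with 4.7.

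The cost is a few sentences. No planned table changes if the 4.7 wording is what was intended.
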